This will be a 6-week, open-label, randomized clinical trial study to compare efficacy and tolerability of the natural treatments omega-3 fatty acids, inositol, and NAC in the treatment of mood dysregulation in children and adolescents with NVLD/ASD. Subjects will include youth ages 5-17 years with a non-verbal learning disability (NVLD) or autism spectrum disorder (ASD) and current symptoms of emotional dysregulation. We will enroll 60 subjects to allow for the randomization of 30 subject into each treatment arm.

The full inclusion and exclusion criteria are included below:

A. Inclusion Criteria:

1. Male or female subjects, 5-17 years of age.
2. A previous established diagnosis of non-verbal learning disability (NVLD) or DSM-V Autism Spectrum Disorder and/ or combined T-scores on the Child Behavior Checklist \geq 195 on the Withdrawn + Social Problems + Thought Problems subscales.

3. Current symptoms of emotional dysregulation as indicated by combined T-scores on the Child Behavior Checklist ≥ 180 on the Anxiety/Depression + Aggression + Attention subscales.
4. Subjects and their caregivers must be English-speaking and have a level of understanding sufficient to communicate intelligently with the investigator and study coordinator, and to cooperate with all tests and examinations required by the protocol.
5. Subjects and their caregivers must be willing and able to comply with all study procedures.
6. Each subject and his/her authorized legal representative must understand the nature of the study. The subject's authorized legal representative must sign an informed consent document and the subject must sign an informed assent document.
7. Subject must be able to swallow pills.
8. Subject must have access to a computer with a camera, speaker, microphone, and internet connection.
9. Subjects must be willing to refrain from treatment changes during the study protocol.

B. Exclusion Criteria:

1. Investigator and his/her immediate family; defined as the investigator's spouse, parent, child, grandparent, or grandchild.
2. Serious or unstable illness including hepatic, renal, gastroenterological, respiratory, cardiovascular (including ischemic heart disease), endocrinologic, neurologic, immunologic, or hematologic disease.
3. History of bleeding diathesis, including those with von Willebrand disease.
4. Uncorrected hypothyroidism or hyperthyroidism.

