Natural Treatments for the Management of Emotional Dysregulation in Youth With Non-verbal Learning Disability (NVLD) and/or Autism Spectrum Disorders (ASD)

NCT03757585

April 23, 2025

Statistical Methods

Participants were included in the analysis based on a modified intent to treat analysis plan with the criterion that participants had to be exposed to the study medications for ?2 weeks. Baseline clinical characteristics were examined using Pearson's chi-squared test for dichotomous measures and truncated Poisson regression models for continuous measures (CBCL-AAA and CBCL-AT: lower level [II] of truncation=150, upper level [ul] of truncation=270; SRS: ll=30, ul=90; BRIEF: ll=30, ul=100; YMRS: ul=60; CDI: ul=40). Primary efficacy measures of mania and depression, as well as secondary measures of autism symptoms and executive functioning, were analyzed using mixed-effects Poisson regression models predict the outcome measure of interest from the study group, study week (continuous), and the study group-by-study week interaction, which is the primary effect of interest. Secondary efficacy measures of mania and depression assessed at endpoint were examined using logistic regression models predicting the outcome of interest from the study group. Adverse events (AEs) were analyzed using a Poisson regression model for AE counts and Fisher's exact tests for AE prevalence. All analyses were two-tailed with an alpha level of 0.05 and conducted using Stata (Version 18.1) (StataCorp, 2023).

We also examined the moderating effect of 1) the CBCL Autistic Traits (AT) profile defined by a combined T-score ?195 on the CBCL Withdrawn/Depressed, Social Problems, and Thought Problems scales, and 2) the CBCL-Bipolar (BP) profile defined by a combined T-score ?210 on the CBCL Aggressive Behavior, Attention Problems, and Anxious/Depressed scales. To examine these moderating effects, we added a 3-way interaction term between study group, study visit, and CBCL profile group to each of the models for the primary and secondary outcomes of interest. The moderating effects of the CBCL-AT and CBCL-BP profiles were examined separately.

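### The SAP tests CBCL moderation only on scores cut at 195 and 210, although it holds the full scores; if moderation is roughly linear, the cut costs real information.

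*SAP*

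**What the plan says.** SAP, Statistical Methods, second paragraph, names two moderators. The first is the autistic-traits profile, a "combined T-score ?195 on the CBCL Withdrawn/Depressed, Social Problems, and Thought Problems scales". The second is "the CBCL-Bipolar (BP) profile defined by a combined T-score" of at least 210, summed over the aggression, attention and anxiety/depression scales. The question mark before 195 stands where the text extraction lost a sign, as it also did before 210; I read both as at least. On the model, the SAP says "we added a 3-way interaction term between study group, study visit, and CBCL profile group to each of the models". This covers every primary and secondary outcome model, with the two profiles examined separately. It describes no version that uses the score itself.

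The first paragraph of the same section analyses baseline characteristics with "truncated Poisson regression models for continuous measures (CBCL-AAA and CBCL-AT: lower level [II] of truncation=150, upper level [ul] of truncation=270". Both sums are therefore held in full and treated as continuous there. The SAP does not expand the label AAA; I read it as the sum of the three scales that define the bipolar profile.

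The protocol uses the same sums at entry. Inclusion criterion 3 requires "Current symptoms of emotional dysregulation as indicated by combined T-scores on the Child Behavior Checklist" of at least "180 on the Anxiety/Depression + Aggression + Attention subscales". Under criterion 2, an autistic-traits sum of at least 195 is one and/or route, beside an established diagnosis of NVLD or ASD. Planned enrolment is 60, with 30 per arm. The SAP's modified intention-to-treat set also sets a minimum exposure of two weeks, so the analysed number may be smaller.

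**The concern.** Cutting a score treats every child on one side as the same. For the bipolar profile, 180 and 209 count as equal, while 209 and 210 count as different. If the treatment difference changes gradually with the score, the yes/no version captures only part of that gradient.

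Tests of interaction are weak in a trial of this size, so the loss matters more here than it would for a main effect. The precision of a cut moderator also depends on how many children happen to fall on each side. The autistic-traits cut coincides with an entry route, so that split in particular may be uneven. A null result could then say little, and a positive one could rest on a few children near the cut.

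**Working it through.** **Inputs from the documents.** Cuts at 195 and 210; score range 150 to 270; entry floor of 180 on the AAA sum; 60 children, 30 per arm; two-sided alpha 0.05. The documents give no power, mean, SD or share above either cut for these analyses, so there is no stated figure to reproduce. The share above the cut, p, is an assumption throughout.

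**Step 1: information kept.** For a normal score and linear moderation, the efficiency of the cut relative to the full score is their squared correlation, r² = φ(c)² / [p(1 − p)]. Here c is the standard normal cut point that leaves a share p above it, and φ is the normal density.

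- At 50/50: 0.3989² / 0.25 = 0.637, a loss of 36%.
- At 20/80: 0.2800² / 0.16 = 0.490, a loss of 51%.

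**Step 2: power.** An 80% test has a standardised effect of 1.960 + 0.842 = 2.802. After the cut, power is Φ(2.802·√r² − 1.960).

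- At 50/50: Φ(2.802 × 0.798 − 1.960) = Φ(0.275) = 61%.
- At 20/80: Φ(2.802 × 0.700 − 1.960) = Φ(0.001) = 50%.

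| Assumed split | r² | Loss | Power, if 80% on the score |
|---|---|---|---|
| 50/50 | 0.637 | 36% | 61% |
| 30/70 | 0.576 | 42% | 57% |
| 20/80 | 0.490 | 51% | 50% |
| 10/90 | 0.342 | 66% | 37% |

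**Step 3: other score shapes.** These come from simulation with 400,000 draws per setting and assumed latent SDs of 15 to 25.

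- AAA sum, normal truncated to 180–270, cut at 210, latent means 190 to 220: loss 32% to 50%.
- Autistic-traits sum, normal truncated to 150–270, cut at 195, latent means 180 to 220: loss 34% to 79%. The largest losses occur where nearly all children lie above the cut.
- Uniform score, r² = 3p(1 − p): loss 1 − 0.75 = 25% at 50/50 and 1 − 0.48 = 52% at 20/80.

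**Step 4: what the profile contrast can detect.** Take one summary value per child, 80% power, and 30 per arm. The smallest detectable difference in treatment effect between profile groups is 2.802 × √{2[1/(30p) + 1/(30(1 − p))]} SD.

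- At 50/50 (15 and 15 per arm): 2.802 × √0.267 = 1.45 SD.
- At 20/80 (6 and 24 per arm): 2.802 × √0.417 = 1.81 SD.

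**Limit of the calculation.** It treats the analysis as an ordinary linear regression. The SAP's models are mixed-effects Poisson and logistic, so the figures indicate size only.

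**The case against.** The strongest defence is that the profile is itself the question. Both cuts define named profiles, 195 is also an entry threshold, and neither looks chosen from the data. If moderation really switches at the cut, the split loses nothing. A linear score term would then be the less efficient test, by the same r². This stands, and it is why the profile models should be kept. It does not justify making them the only test, since the SAP offers no reason to expect a switch.

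A second objection also stands. The SAP is dated April 2025 and written in the past tense, so the analyses may already have been run. Promoting a different moderator analysis after seeing results would itself be post hoc.

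Several stronger readings are tempting but unsupported:

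- A reader might infer that the plan is known to discard a third to over half of the moderator information, or that 60 children are worth some fixed smaller number. Any such figure depends on linear moderation, the score's shape and the split, none of which the documents give. Step 3 shows losses both below and above that range.
- A reader might infer that the 210 cut divides a narrow range. The entry floor still leaves 180 to 270, which is 90 of the 120 points.
- A reader might call this the weakest test in the plan. No power is given for any test, so it cannot be ranked.
- A reader might infer that the main conclusion is at risk. The SAP names the group-by-week interaction as the effect of primary interest, and moderation is additional to it.

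**Conclusion.** The point holds as a conditional one. The SAP tests moderation only on dichotomised scores while holding the continuous sums and treating them as continuous elsewhere in the same section. Under roughly linear moderation and roughly normal scores, the loss is about 36% at an even split and about 51% at 20/80. In every truncated-normal setting in Step 3 it was at least about 32%. It is smaller for a uniform score split evenly (25%), and nil if moderation switches at the cut. This is a worthwhile improvement to an additional analysis, not a flaw in the primary comparison.

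**What to change.** Add a moderator analysis that uses the centred continuous CBCL-AAA and CBCL-AT sums, each in its own model with all lower-order terms:

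- In the mixed-effects Poisson models, test group-by-week-by-score.
- In the endpoint logistic models, test group-by-score. Those models predict the outcome from study group and have no week term, so a three-way term with time cannot be fitted there.

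Keep the SAP's profile models alongside. For clinical readers, show model-based treatment contrasts at stated scores below and above 195 and 210. Report the number of children on each side of each cut, by arm, so that the actual split replaces the assumed ones above.

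If results have already been seen, label the continuous analysis as added afterwards and leave the profile analysis in its planned place.

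No new data are needed. The cost is SAP wording and a little more analysis work, with additional model runs if the analyses are already complete. The downside is the assumption that the score effect is approximately linear on the link scale (log for Poisson, logit for logistic), and the continuous result is harder to read than a two-group contrast.
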